5.9.3 Exploratory Analysis

5.9.3.1 Tumor Biomarker Analysis

CCI

CCI

5.9.3.2 Germline DNA Polymorphism Analysis

CCI

5.10 Safety Analyses

These analyses will be performed using the Safety population.

5.10.1 Adverse Events

5.10.1.1 Adverse Events

AEs will be coded using the Medical Dictionary for Regulatory Activities (MedDRA).

Treatment-emergent is defined as any AE that occurs after administration of the first dose of study treatment and up through 30 days after the last dose of study drug or until start of subsequent antineoplastic therapy; any event that is considered drug-related regardless of the start date of the event; or any event that is present at baseline but worsens in severity after baseline. Patients who experience the same AE more than once will have that event counted only once within each body system, once within each High Level Term, and once within each Preferred Term.

AEs will be tabulated by System Organ Class, High Level Term, and Preferred Term.

Summary tabulations include the following subsets:

- Treatment-emergent AEs
- Drug-related treatment-emergent AEs

MLN9708**Study C16007 Statistical Analysis Plan**

- Grade 3 or higher treatment-emergent AEs
- Grade 3 or higher drug-related treatment-emergent AEs
- Grade 3 treatment-emergent AEs and Grade 4 treatment-emergent AEs
- Grade 3 drug-related treatment-emergent AEs and Grade 4 drug-related treatment-emergent AEs

Treatment-emergent AEs will be tabulated by System Organ Class, Preferred Term, and highest intensity. The most commonly reported (at least 10% of all patients) treatment-emergent AEs will be presented by Preferred Term. In addition, a by-patient listing of the treatment-emergent AEs will be presented.

AEs with start dates that are completely or partially missing will be analyzed as follows:

- If the start date has a month and year but the day is missing, the event will be considered treatment emergent if both the month and year of the start date of the event are on or after the month and year of the date of the first dose of MLN9708 and on or before the month and year of the date of the last dose of MLN9708 plus 30 days.
- If the start date has a year, but the day and month are missing, the event will be considered treatment emergent if the year of the start date of the event is on or after the year of the date of the first dose of MLN9708 and on or before the year of the date of the last dose of MLN9708 plus 30 days.
- If the start date of an event is completely missing, then the event is assumed to be treatment emergent.

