Relationship to study drug administration will be determined by the investigator responding yes or no to this question: Is there a reasonable possibility that the AE is associated with the study drug?

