1.1 Study Design

This is an open-label, multicenter, phase 1, dose-escalation study of MLN9708 in adult patients with previously treated systemic light-chain (AL) amyloidosis. A 3 + 3 dose-escalation scheme will be implemented. Patients will receive escalating doses of MLN9708 orally (PO) on Days 1, 8, and 15 in a 28-day cycle in the absence of disease progression (PD) or unacceptable toxicity. If there is no hematologic response (complete response [CR], very good partial response [VGPR], or partial response [PR]) after completion of 3 cycles of single-agent MLN9708, dexamethasone will be added on Days 1 to 4 of every cycle (Days 1-4 every 28 days) beginning with Cycle 4. The patient's response status will be reassessed after 3 additional cycles; if there is no hematologic response at that time, the patient will be removed from treatment and followed for survival.

Once the maximum tolerated dose (MTD)/recommended phase 2 dose (RP2D) has been established, 2 expansion cohorts of patients with relapsed or refractory amyloidosis, including approximately 10 proteasome inhibitor-naïve patients and approximately 16 proteasome inhibitor-exposed patients, will be treated at the MTD/RP2D to more fully characterize the safety, tolerability, and efficacy of MLN9708, quality of life (QOL), and the pharmacokinetics (PK) and pharmacodynamics of MLN9708 in this patient population.

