5. STATISTICAL METHODOLOGY

Analyses will be primarily descriptive in nature. No formal statistical tests will be performed. Summary tabulations will be presented that display the number of observations, mean, standard deviation, median, minimum, and maximum for continuous variables, and the number and percentage (calculated using nonmissing values) per category for categorical data, unless specified otherwise.

Patients will be analyzed at the dose level to which they were originally assigned, including those who receive subsequent treatment at a lower dose level.

The analyses for the clinical study report (CSR) will be conducted after 75% of patients have PD or 12 months after last patient is enrolled, whichever occurs first in the study. At that time, all relevant data will be queried and cleaned; a database snapshot will be taken and used for the CSR. Additional follow-up treatment data will be entered into the database through study termination. Analyses may be updated based on additional information. An addendum to the CSR may be written if warranted based on these analyses. If deemed appropriate, however, the sponsor may decide to perform the analyses for CSR at the end of the study (EOS), which is approximately 2 years after the last patient is enrolled.

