5.1 Sample Size Justification

A 3 + 3 dose-escalation scheme will be conducted, with 3 to 6 DLT-evaluable patients evaluated at each dose level. It is expected that as many as 30 patients will be enrolled in the dose-escalation part of this study.

Once the MTD/R2PD has been established, the following 2 expansion cohorts will be treated at the MTD or RP2D:

1. Proteasome inhibitor-naïve expansion cohort including approximately 8 organ response-evaluable patients. There will be approximately 83% probability of observing at least 2 patients with organ responses among 8 patients based on the binomial probability calculation if the overall organ response rate is 35% for this population. Approximately 10 patients will be enrolled to obtain 8 response-evaluable patients.
2. Proteasome inhibitor-exposed expansion cohort including approximately 14 organ response-evaluable patients. There will be approximately 80% probability of observing at least 2 patients with organ responses among 14 patients based on the binomial probability calculation if the overall organ response rate is 20% for this population. Approximately 16 patients will be enrolled to obtain 14 organ response-evaluable patients.

Proteasome inhibitor-naïve patients are the patients who have not received any prior bortezomib contained therapy and the proteasome inhibitor-exposed patients are the patients who received at least one prior bortezomib contained therapy. Because approximately 6 patients in the dose-escalation part of the study will be included in the expansion cohorts, approximately 20 patients will be enrolled in the expansion part of this study. Please note that this is only for sample size justification, and the sponsor can stop the study enrollment for expansion cohorts at any time if deemed appropriate.

Overall, as many as 50 patients will be enrolled in this study.

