5.8.2 Efficacy Analyses

The hematologic response (CR, VGPR, PR, no change [NC], PD) rate will be tabulated and analyzed based on the Hematologic Response-Evaluable population and presented with a 2-sided 95% exact binomial confidence interval. In addition, the overall hematologic response rates up to the end of Cycle 3 and up to the end of Cycle 6 will also be tabulated and analyzed in a similar way.

Vital organ response rate will be tabulated and analyzed based on the Organ Response-Evaluable population. Organ-specific response rate will be tabulated and analyzed based on in the subgroup of the Organ Response-Evaluable population with amyloid involvement of the specific organ at baseline. Estimates of the organ response rate will be presented with 2-sided 95% exact binomial confidence intervals.

MLN9708**Study C16007 Statistical Analysis Plan**

Best hematologic response, time to hematologic response, time to best hematologic response, duration of hematologic response, time to hematologic PD, hematologic PFS, and OS will be presented in a by-patient listing. Vital organ response, organ-specific response, time to vital organ response, duration of vital organ response, time to organ PD, organ PFS, and OS will be presented in a by-patient listing.

Time to hematologic response, time to best hematologic response, duration of hematologic response, time to hematologic PD, hematologic PFS, and OS (1-year OS rate) will be analyzed using standard survival analysis techniques based on Kaplan-Meier estimates, if appropriate.

Raw values of serum M-protein, urine M-protein, serum free light chain (FLC), and the difference between amyloid-forming and nonamyloid-forming free light chain (dFLC), as well as the change from baseline, will be presented in by-patient listings. A waterfall plot will be generated to display the maximum change from baseline in dFLC.

QOL will be assessed for patients in the expansion cohorts only using the European Organisation for Research and Treatment of Cancer Quality of Life Questionnaire-Core 30 (EORTC-QLQ-C30, multiple myeloma module). Descriptive statistics will be presented for both the actual values and the changes from baseline in EORTC-QLQ-C30 assessment over time. EORTC-QLQ-C30 assessments will be analyzed to determine if hematologic response to therapy is accompanied by measurable improvement in QOL.

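### Cumulative adverse event tables and vital organ response pool MLN9708 alone with MLN9708 plus dexamethasone, with no split at the first dexamethasone dose

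*SAP*

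**What the plan says.** **Treatment.** For patients without a hematologic response after three single-agent cycles, SAP 1.1 states that "dexamethasone will be added on Days 1 to 4 of every cycle", starting with Cycle 4. Protocol 4.1 says the same.

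**Primary endpoint.** Protocol 3.1 lists AEs, SAEs, laboratory values and neurotoxicity of oral MLN9708.

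**AE outputs.** SAP 5.10.1.1 defines the window: "Treatment-emergent is defined as any AE that occurs after administration of the first dose of study treatment and up through 30 days" past the final dose, or until subsequent antineoplastic therapy. The SAE tables (5.10.1.2) and the tables of AEs leading to discontinuation or modification (5.10.1.4) have no period split. SAP 5.4.4 groups patients by dose level, pooled dose levels, expansion cohort, MTD and overall. SAP 5 keeps each patient under the dose first assigned. Dexamethasone exposure is summarized only as a number of cycles (5.7.2.1).

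**Efficacy outputs.** SAP 5.8.2 says that "the overall hematologic response rates up to the end of Cycle 3 and up to the end of Cycle 6 will also be tabulated". Organ response (5.8.1) has two time frames, to the EOT visit and to a new antineoplastic therapy or study end. Both span dexamethasone cycles.

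**Attribution.** Protocol 10.2 asks one yes/no question: "Is there a reasonable possibility that the AE is associated with the study drug". Protocol 6.6 uses the term *study drug* for either agent and asks for attribution to one of them when possible, to guide dose modification.

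**The concern.** The primary endpoint is stated for MLN9708, but from Cycle 4 some patients take two drugs and their events stay under the MLN9708 dose level. Protocol Table 6-5 covers edema, confusion or mood alteration, muscle weakness, hyperglycemia and gastrointestinal events as dexamethasone-related. Protocol 1.3 also lists peripheral edema among effects that may be due to MLN9708 or to the disease, so the two profiles overlap.

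The counting rules hide the switch. SAP 5.10.1.1 counts a repeated event once per term and adds a table by highest intensity. Edema of Grade 1 before dexamethasone and Grade 3 after it would appear there as one Grade 3 event at the MLN9708 dose level.

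Two uses are at stake. Protocol 6.4 bases the RP2D partly on Grade 3/4 AEs, SAEs, treatment discontinuation and toxicity from Cycle 2 on, which can include dexamethasone cycles. The expansion cohorts are sized on organ response, and a response first seen after dexamethasone would count the same as one on MLN9708 alone.

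**Working it through.** **1. The plan's own figures.** SAP 5.1 gives, for the proteasome inhibitor-naive cohort, "There will be approximately 83% probability of observing at least 2 patients with organ responses among 8 patients" "if the overall organ response rate is 35% for this population". For the exposed cohort it gives about 80% for at least 2 among 14 "if the overall organ response rate is 20% for this population". With P(X ≥ 2) = 1 − (1−p)^n − n·p·(1−p)^(n−1):

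- Naive: 1 − 0.65^8 − 8 × 0.35 × 0.65^7 = 1 − 0.0319 − 0.1373 = 0.831.
- Exposed: 1 − 0.80^14 − 14 × 0.20 × 0.80^13 = 1 − 0.0440 − 0.1539 = 0.802.

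Both reproduce. The point disputes neither figure.

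**2. Which outputs mix the regimens.** Dexamethasone cannot start before Cycle 4.

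| Output | Place | Mixed? |
|---|---|---|
| DLT listing and MTD | SAP 2.2, 5.10.1.5 | No, Cycle 1 |
| PK and pharmacodynamics | Protocol 7.5.13 | No, Cycle 1 |
| Hematologic response to end of Cycle 3 | SAP 5.8.2 | No |
| ECG intervals and vital signs | SAP 5.10.4, 5.10.5 | Readable by time point |
| Dose modifications | SAP 5.7.2.2 | By cycle if data suffice |
| AEs, SAEs, AEs leading to discontinuation or modification | SAP 5.10.1.1, 5.10.1.2, 5.10.1.4 | Yes |
| Vital organ response | SAP 5.8.1, 5.8.2 | Yes |
| Later-cycle data for the RP2D | Protocol 6.4 | Can be |

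**3. Illustration for an AE.** All inputs are assumed. Let p be the event rate on MLN9708 alone, d the share of patients adding dexamethasone, and x the share of those still event-free who first have the event afterwards. Taking dexamethasone use as independent of earlier events:

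pooled rate = p + (1 − p)·d·x

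- p = 10%, d = 30%, x = 10%: 0.10 + 0.90 × 0.30 × 0.10 = 12.7%.
- p = 10%, d = 70%, x = 30%: 0.10 + 0.90 × 0.70 × 0.30 = 28.9%.
- p = 20%, same extremes: 22.4% and 36.8%.

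The pooled figure exceeds the pre-dexamethasone one by about 2 to 19 percentage points. Not all of that is a dexamethasone effect, because some of these events could have occurred on continued MLN9708 alone.

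**4. Illustration for organ response.** SAP 5.1 does not say whether its assumed rates include responses after dexamethasone. Suppose they do, and a share f arises only after it. The single-agent rate is then (1 − f) times the assumed rate:

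| f (assumed) | Naive rate | P(≥2 of 8) | Exposed rate | P(≥2 of 14) |
|---|---|---|---|---|
| 10% | 31.5% | 77% | 18% | 75% |
| 25% | 26.3% | 66% | 15% | 64% |
| 50% | 17.5% | 42% | 10% | 42% |

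These rows show sensitivity only. The documents give no value for f.

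**The case against.** The study is descriptive ("No formal statistical tests will be performed"), and response-adapted dexamethasone is part of the protocol regimen, so tabulating the whole regimen is a defensible convention. By-patient listings of AEs and SAEs are planned, and Protocol 8.1.8 allows additional safety analyses. This is a reason to keep the overall tables. It does not supply the missing summary: listings are not a tabulation, and an optional analysis is not a specified one.

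A reader might infer more than the documents support:

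- *That the whole primary safety profile or the MTD is confounded.* DLTs and the MTD rest on Cycle 1, before any dexamethasone. The RP2D uses Cycle 1 data from 6 evaluable patients plus later data, so it is exposed only in part.
- *That hematologic response is the only result shown for the single-agent period.* This is true of efficacy outcomes only, as the table of outputs shows.
- *That attribution cannot separate the agents.* Protocol 6.6 asks for per-agent attribution when possible, and Protocol 6.14 calls the MLN9708 capsules the study drug. On that narrow reading the drug-related tables already concern MLN9708. What stands is ambiguity.
- *That every non-responder after Cycle 3 receives dexamethasone.* Patients who stop first for progression or toxicity do not.
- *That later infections point to dexamethasone.* Infection is not in Table 6-5, and Protocol 1.2.3 ties infection risk to MLN9708's own lymphoid and blood-count effects.

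The last objection concerns the remedy, and it stands. A before/after split does not isolate MLN9708, because dexamethasone goes only to non-responders and only at later cycles. Counts by period will be small.

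**Conclusion.** The point holds within limits. The cumulative AE, SAE and AE-discontinuation/modification tables and vital organ response cannot be read as results of MLN9708 alone. This affects the cumulative part of the primary safety endpoint and any later-cycle data used for the RP2D.

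The size cannot be fixed from the documents, which do not state how many patients add dexamethasone. Under the assumed ranges, a 10% event rate on MLN9708 alone would read about 13-29% when pooled. The range rests on the assumed 30-70% adding dexamethasone and 10-30% new events among those still event-free.

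This is an inexpensive improvement to interpretation. No planned figure is wrong.

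**What to change.** **SAP 5.10.1.** Keep the overall tables. For all dose levels pooled and for the MTD/RP2D group, add columns by onset: before the first dexamethasone dose (all patients, time truncated at that dose) and on or after it. Do this for:

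- treatment-emergent AEs
- drug-related treatment-emergent AEs
- Grade 3 or higher treatment-emergent AEs
- SAEs
- AEs leading to discontinuation

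Show patient-months at risk for each period. Add a rule for partial onset dates and one for events that begin before dexamethasone and worsen after it. State which agent or agents *drug-related* covers.

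**SAP 5.8.2.** Classify each vital organ response as first documented before dexamethasone, after it, or in a patient who never received it.

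**Labelling.** Call both displays descriptive, since period is mixed with time on drug and hematologic response status. Note that for patients who add dexamethasone at Cycle 4, only the scheduled post-Cycle 3 organ assessment (Protocol 7.5.12.2) precedes it. Protocol 1.1.1 expects organ improvement to be potentially slow, so single-agent organ response will read low.

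**Cost.** Extra programming and sparse period counts, assuming first dexamethasone dates are recorded; the SAP commits only to counting dexamethasone cycles. Sample size and conduct do not change.

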5.10.1.2 Serious Adverse Events

The number and percentage of patients experiencing at least 1 treatment-emergent serious AE (SAE) will be summarized by MedDRA System Organ Class, High Level Term, and Preferred Term. A similar table for drug-related SAEs will also be presented.

A by-patient listing of the SAEs will be presented (the listing will contain all SAEs regardless of treatment-emergent AE status).

5.10.1.3 Deaths

A listing of on-study deaths will be presented. On-study death is defined as death events that occur within 30 days of the last dose of study drug.

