4. STUDY DESIGN

4.1 Overview of Study Design

This is a phase 1, open-label, multicenter clinical study using the oral formulation of MLN9708 in patients with previously treated systemic AL amyloidosis who require further therapy. As many as 30 patients will be enrolled in the dose-escalation portion of the study, and as many as 20 patients will be enrolled in the expansion cohorts. Overall, as many as 50 patients will be enrolled.

The dose-escalation portion of the study will be aimed at determining the safety profile and the MTD/RP2D of MLN9708 administered weekly in patients with previously treated AL amyloidosis. Patients will receive escalating doses of MLN9708 PO on Days 1, 8, and 15 in a 28-day cycle in the absence of disease progression or unacceptable toxicity.

Once the MTD/RP2D has been established, 2 expansion cohorts of patients with relapsed or refractory amyloidosis, including approximately 10 proteasome inhibitor-naïve patients and approximately 16 proteasome inhibitor-exposed patients, will be treated at the MTD/RP2D to more fully characterize the safety, tolerability, and efficacy of MLN9708, and the PK and

pharmacodynamics of MLN9708 in this patient population. As many as 30 patients will be enrolled in the dose-escalation portion of the study, and as many as 20 additional patients (26 in total, including 6 patients from the dose-escalation portion) will be enrolled in the expansion cohorts.

The estimated safe starting dose of MLN9708 will be selected from the dose-escalation portion of the C16004 study, an ongoing phase 1 study of weekly dosing in patients with relapsed and refractory multiple myeloma. The starting dose will be at least 1 dose level below the C16004 MTD if it has been reached by the time this study starts, and if not, then a dose level completed without documented DLTs.

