6.5.2 Criteria for Toxicity Recovery Before Beginning the Next Cycle of Treatment

If a patient fails to meet the criteria outlined in the following sections for beginning the next cycle of treatment, initiation of the next cycle should be delayed for 1 week. At the end of that time, the patient should be re-evaluated to determine whether the criteria for retreatment have been met. If the start of the next cycle needs to be delayed for more than 2 weeks due to incomplete recovery from treatment-related toxicity, refer to the recommended dose modification guidelines provided in Section **6.6**. The maximum delay before treatment should be discontinued will be 3 weeks (except in the case of investigator determined clinical benefit and discussion with the Millennium clinician).

NOTE: A delay of more than 2 weeks because of lack of adequate recovery of MLN9708-related hematologic or nonhematologic toxicities occurring during Cycle 1 meets the criteria for a DLT in the given cohort (refer to Section **6.3**). If the patient is to receive additional treatment despite a DLT, the dose of MLN9708 will be reduced by at least 1 dose level (or by 33% if the patient is receiving the first dose level) upon resolution of toxicity (refer to Section **6.6**).

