6.6.1 MLN9708 Dose Adjustments for Hematologic Toxicity

Dosage adjustments for hematologic toxicity are outlined in [Table 6-2](#).

Table 6-2 MLN9708 Dose Adjustments for Hematologic Toxicities

Criteria	Action
Within-Cycle Dose Modifications	
If platelet count $\leq 30 \times 10^9/L$ or ANC $\leq 0.75 \times 10^9/L$ on a MLN9708 dosing day (other than Day 1)	MLN9708 dose should be withheld. Complete blood count (CBC) with differential should be repeated at least every other day until the ANC and/or platelet counts have exceeded the prespecified values (see Section 6.5.2.1) on at least 2 occasions. In the event CBC cannot be repeated at least every other day, dose modifications should be made in consultation with sponsor. Upon recovery, MLN9708 may be reinitiated with 1 dose level reduction or by 33% if the patient is receiving the first dose level.
Dose Modifications for Subsequent Treatment Cycles	
Delay of > 2 weeks in the start of a subsequent cycle due to lack of toxicity recovery as defined in Section 6.5.2 :	
 - Hold MLN9708 until resolution as per criteria Section 6.5.2. - Reduce MLN9708 1 dose level or 33% if the patient is receiving the first dose level. - The maximum delay before treatment should be discontinued (except in the case of investigator determined clinical benefit and discussion with the Millennium clinician) will be 3 weeks.
Dose Modifications for Subsequent Treatment Cycles	
All hematologic toxicities	For hematologic toxicity that occurs during a cycle but recover in time for the start of the next cycle, a dose level reduction will be made either based on within-cycle or for

Table 6-2 MLN9708 Dose Adjustments for Hematologic Toxicities

Criteria	Action
	subsequent cycle criteria, but not for both from the same cycle.

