10.3 Monitoring of Adverse Events and Period of Observation

AEs, both nonserious and serious (which include all deaths), will be monitored throughout the study as follows:

- AEs will be reported from the first dose of study drug through 30 days after administration of the last dose of study drug or the start of subsequent antineoplastic therapy, whichever occurs first, and recorded in the eCRFs. That is, if a patient begins a new antineoplastic therapy, the AE reporting period for nonserious AEs ends at the time the new treatment is started.
- Serious pretreatment events will be reported to Millennium Pharmacovigilance or designee from the time of the signing of the informed consent form (ICF) up to first dose of study drug, but will not be recorded in the eCRF.
- SAEs will be reported to Millennium Pharmacovigilance or designee from the first dose of study drug through 30 days after administration of the last dose of study drug and recorded in the eCRF. All SAEs should be monitored until they are resolved or are clearly determined to be due to a patient's stable or chronic condition or intercurrent illness(es). Any SAE that occurs at any time after completion of the study and the designated follow-up period that the investigator considers to be related to study drug must be reported to the Millennium Department of Pharmacovigilance.

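### The SAP's death listing stops 30 days after the last dose, so it omits drug-related deaths after day 30 and deaths late in a permitted dosing gap of up to 35 to 49 days

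*SAP*

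**What the plan says.** SAP 5.10.1.3 has two sentences. The first sets the output: "A listing of on-study deaths will be presented". The second sets its scope: "On-study death is defined as death events that occur within 30 days of the last dose of study drug". Neither asks whether the patient had stopped treatment or whether the death was judged drug-related. SAP 5.10.1.1, in the same part of the plan, does use relatedness: its treatment-emergent definition takes in "any event that is considered drug-related regardless of the start date of the event".

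The dosing rules are in the protocol:

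- Section 4.1: "Patients will receive escalating doses of MLN9708 PO on Days 1, 8, and 15 in a 28-day cycle".
- Table 6-2 (section 6.6.1), for low counts on a dosing day other than Day 1: "MLN9708 dose should be withheld". No limit on consecutive withheld doses is stated there.
- Section 6.5.2, on waiting for toxicity recovery before the next cycle: "The maximum delay before treatment should be discontinued will be 3 weeks". The exception reads "except in the case of investigator determined clinical benefit and discussion with the Millennium clinician".

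Two other routes can show a death. SAP 5.10.1.2 plans a by-patient listing of all SAEs, plus tables of treatment-emergent and drug-related SAEs. SAP 5.8.2 plans by-patient listings that include OS. Protocol 10.3 has SAEs entered in the eCRF through 30 days after the last dose, and adds: "All SAEs should be monitored until they are resolved or are clearly determined to be due to a patient's stable or chronic condition". Related SAEs arising after the study and its follow-up period go to Pharmacovigilance. The section does not say that these are also entered in the eCRF.

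**The concern.** The window is counted from the last dose received, not from the end of treatment. In a schedule with a planned rest week, withheld doses and a 3-week permitted delay, the two can be far apart. A patient waiting to restart is still under study treatment, but after day 30 a death in that patient no longer counts as on-study. Patients in this position have toxicity that has not resolved, so they are not a random subset.

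The missing relatedness clause creates a second gap and an inconsistency within the SAP: a fatal event can be treatment-emergent because it is drug-related and still be absent from the death listing.

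Safety and tolerability are primary objectives (Protocol 2.1). Protocol 1.1.1 notes that most patients with this disease die of cardiac causes, often suddenly, so attribution is hard. A reader of the study report needs every death set out with its timing and relationship.

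**Working it through.** The documents state no dose-gap figure, so there is none to reproduce. The check is calendar arithmetic.

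**Inputs.** Doses on Days 1, 8 and 15, so the next cycle is due on Day 29 (Protocol 4.1). Cycle delay of 0 to 21 days (Protocol 6.5.2), assumed to run from the planned Day 29. Window of 30 days (SAP 5.10.1.3).

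**Formula.** Gap = (29 − day of last dose) + delay. Days outside the window = gap − 30, if positive.

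| Last MLN9708 dose | No delay | 1 week | 2 weeks | 3 weeks | Days outside window at 3 weeks |
|---|---|---|---|---|---|
| Day 15 | 14 | 21 | 28 | 35 | 35 − 30 = 5 |
| Day 8 (Day 15 withheld) | 21 | 28 | 35 | 42 | 42 − 30 = 12 |
| Day 1 (Days 8 and 15 withheld) | 28 | 35 | 42 | 49 | 49 − 30 = 19 |

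The last column counts from day 31 through the day on which the delay reaches its limit. As shares of the whole gap: 5/35 = 14%, 12/42 = 29%, 19/49 = 39%. Under the clinical-benefit exception the gap has no stated upper limit.

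These gaps include planned rest days; the delay itself is at most 21 days. Six of the twelve combinations stay within 30 days, including every delay of up to 2 weeks when the Day 15 dose was given.

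**Dexamethasone.** If it counts as study drug (Protocol 6.6 uses the term that way), a patient in Cycle 4 or later who takes it on Days 1 to 4 has a last dose on Day 4. The longest gap is then 50 − 4 = 46 days, with 16 outside the window. The 35- and 42-day cases do not change.

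**Where each type of death appears** (no subsequent antineoplastic therapy assumed):

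| Death | Death listing | SAE outputs (SAP 5.10.1.2) | OS listing |
|---|---|---|---|
| Within 30 days of last dose | Yes | Yes | Yes |
| After day 30, from an SAE that began within the window | No | Yes | Yes |
| After day 30, event began after day 30, judged related | No | Only if the late report reaches the database | Yes |
| After day 30, event began after day 30, judged unrelated, patient not yet discontinued | No | No, outside SAE collection | Yes, with no cause specified |

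The second row includes, for example, an event that starts on day 20 and is fatal on day 33. The last two rows are the deaths for which no planned output is sure to show cause and relationship.

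**The case against.** The strongest reply is that the safety section does not depend on this listing. Death is a seriousness criterion (Protocol 10.1.3), and SAP 5.10.1.2 lists all SAEs whether or not they are treatment-emergent. A fatal SAE that began on treatment is therefore shown whatever the date of death, and a late related one is shown once it is in the database. The 30-day window also matches the protocol's AE and SAE collection period, so it is not arbitrary. All of this stands, and it confines the point to the death listing and the last two rows of the second table.

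A reader might infer that deaths during toxicity holds drop out as a class. The calendar does not support that: only deaths more than 30 days after the last dose are lost, and most shorter delays end sooner.

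A reader might also infer that the RP2D could be chosen with treatment-related deaths out of sight. The documents do not support that either. Protocol 6.4 bases the RP2D on Cycle 1 DLTs, Grade 3/4 AEs, SAEs, neuropathy, discontinuations and efficacy. SAP section 4 provides for ongoing safety review. Under Protocol 6.3.1, a delay of more than 2 weeks in starting Cycle 2 for MLN9708-related toxicity is already a DLT. One death among about 26 patients at the RP2D would be 1/26 = 3.8 percentage points, but that only converts a single hypothetical event into a rate. It says nothing about how likely the event is.

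Finally, cause may not exist for some late deaths. Protocol 7.5.17 lets survival status come from telephone, mail or public indexes, and Protocol 10.2 asks one yes/no question about study drug. This limits what the fix can deliver but does not remove the reason for it.

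**Conclusion.** The point holds as a limited gap in safety reporting. As written, SAP 5.10.1.3 would leave off the death listing a death in the last 5, 12 or 19 days of a 35-, 42- or 49-day gap in a patient who has not discontinued, and any drug-related death after day 30. The second omission does not fit the SAP's own treatment-emergent rule. For most such deaths another output exists. For those from events that begin after day 30, cause and relationship are not sure to appear anywhere.

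The figures assume that the 3-week delay runs from Day 29 and that the last dose means MLN9708. The 42- and 49-day cases also require withheld doses followed by the full delay, so they are upper bounds for unusual courses. The number of deaths affected cannot be estimated from the documents and may be zero. No primary estimate, DLT count or sample size depends on it.

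**What to change.** Replace SAP 5.10.1.3 with wording to this effect:

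> All deaths in the Safety population will be listed by dose level, with days from first and last dose, whether treatment had been permanently discontinued, and cause and relationship to study drug where available. A death is on-study if it occurs before permanent discontinuation of treatment, or within 30 days of the last dose, or at any time from an AE that began in that period or is considered drug-related.

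This brings the definition into line with SAP 5.10.1.1. The text should also say whether dexamethasone counts when the last dose is dated.

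The cost is SAP wording and one wider listing; death dates are already followed for OS. There are two downsides. The on-study death count may rise slightly, and cause may be missing for deaths found only through OS follow-up, which is why the wording says where available.
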